**Specific Aims:**

The primary objective of this study is to identify whether a smaller dose of spinal bupivacaine combined with fentanyl reduces the incidence of maternal hypotension and fetal bradycardia in laboring parturients receiving combined spinal-epidural analgesia.

The secondary objective is to evaluate the adequacy of pain relief with the reduced dose of spinal anesthetic.

Outcomes to be measured include:

1. Maternal hypotension. Defined as 20% decrease in systolic blood pressure (when compared with baseline) or a systolic blood pressure less than 100 mm Hg.
2. Fetal bradycardia. Defined as a fall in heart rate to less than 110 bpm, or a prolonged deceleration defined as a fall in heart rate to less than 110 bpm lasting more than 2 minutes.
3. The need to administer ephedrine, phenylephrine, terbutaline, or nitroglycerin to support blood pressure and/or improve the fetal heart rate following the spinal dose
4. Adequacy and duration of pain relief following the spinal using a numeric pain rating scale from zero to ten.
5. Mode of Delivery- Normal spontaneous vaginal delivery, vacuum assisted/forceps, or caesarean section

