After randomization, a baseline pain score on a scale of 0-10 will be obtained. The fetal heart rate tracing will be recorded for 15 minutes with an external continuous heart rate monitor prior to placing the CSE in order to obtain an adequate baseline. Patients will be seated for the placement of the CSE. A blood pressure cuff and pulse oximeter will be in place and an initial blood pressure will be taken. The time of the spinal injection will be recorded. After placement of the CSE, the patient will be placed on her side, as is customarily done. Blood pressure will be taken every 2 minutes for 20 minutes and then every 15 minutes. A continuous fetal heart rate monitor will record the readings electronically. Blood pressure readings will be

recorded again at 60 minutes. All patients will be given our standard PCEA with a continuous infusion of 12ml/hr of 0.0625% bupivacaine with 2mcg/ml fentanyl.

If hypotension and/or fetal bradycardia occur the patient will be treated with ephedrine, phenylephrine, nitroglycerin, or terbutaline as per our standard practice. The dose and timing of this will be recorded.

Patients will also be asked to evaluate the effectiveness of their pain relief by asking them to rate their pain on a scale from 0-10 at 8 minutes (*time to full effect of the spinal dose*) and 60 minutes (*time when spinal dose could start wearing off*) following the spinal dose.

In the event that the patient does not receive adequate pain relief, additional local anesthetic will be administered into the epidural catheter until the patient achieves comfort.

The data form is attached as Appendix B.

Data collected will consist of:

- Demographics: Patient age, gestation, dilation in centimeters, gravity, parity
- Presence of labor induction/augmentation with Pitocin
- Maternal blood pressure- a baseline blood pressure and every 2 minutes for 20 minutes following the dose of spinal bupivacaine. A final blood pressure will also be recorded at 60 minutes.
- Fetal heart rate- a baseline fetal heart rate, and a continuous recording following the dose of spinal bupivacaine with an external monitor
- Cumulative ephedrine, phenylephrine, nitroglycerin, or terbutaline use and timing
- Pain scores at baseline, 8 minutes, and 60 minutes
- Delivery outcomes: normal spontaneous vaginal delivery, vacuum/forceps assisted vaginal, or caesarean section

Statistical Analysis:

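### Two outcome definitions in the primary objective need tightening: the 2-minute fetal limb has no effect, and a systolic pressure below 100 mm Hg counts even in a woman who started below 100

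*Combined protocol and SAP*

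**What the plan says.** The primary objective (Specific Aims) asks whether a smaller spinal bupivacaine dose lowers the incidence of maternal hypotension and fetal bradycardia. The outcome list in that section defines both.

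- **Fetal bradycardia (outcome 2):** "a fall in heart rate to less than 110 bpm, or a prolonged deceleration defined as a fall in heart rate". The first limb has no duration. The second has the same threshold and adds one: "less than 110 bpm lasting more than 2 minutes".
- **Maternal hypotension (outcome 1):** a 20% drop in systolic pressure (SBP) relative to baseline, "or a systolic blood pressure less than 100 mm Hg". Only the 20% limb refers to baseline.

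On measurement, Experimental Design and Method says that before the block "an initial blood pressure will be taken", with no minimum value; pressure is then read every 2 minutes for 20 minutes and less often afterwards. For the fetus, "The fetal heart rate tracing will be recorded for 15 minutes with an external continuous heart rate monitor prior to placing the CSE", followed by "a continuous recording following the dose of spinal bupivacaine with an external monitor". The exclusion criteria (Human subjects) remove women with pre-eclampsia, past pregnancy-induced hypertension or a non-reassuring trace before the block. They do not remove women with low baseline pressure.

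**The concern.** Outcome 2 names a prolonged deceleration and gives it a duration, which suggests that duration mattered to the authors. Joined by *or* to a limb with the same threshold and no duration, that criterion has no effect. The definition therefore does not say whether the event of interest is any dip or a sustained one. If this stays open, the choice could be made after the doses are known.

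In outcome 1, a woman whose pressure was below 100 mm Hg before the spinal, and is below 100 at any later reading, is an event even if her pressure never fell. No dose can prevent that event. The plan expects hypotension in only 3-5% at the lower doses, so even a few automatic events per group are large beside the signal. Randomisation spreads them evenly in expectation. The cost is a diluted contrast, not a bias towards one arm.

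**Working it through.** **The plan's own figure.** The power analysis contains no calculation based on these definitions. Its ANOVA output does reproduce: λ = f²·N·m / (1 + (m − 1)ρ) = 1.2472191² × 9 × 4 / 2.5 = 22.40; critical F(2, 6) = 5.143; power = 0.904. No event rate enters it, so it neither depends on the definitions nor protects against the problem.

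**Fetal rule.** Let A be a fall below 110 bpm, and B a fall below 110 bpm lasting more than 2 minutes. Every B is an A, so (A or B) = A. Deleting B changes no classification.

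**Maternal rule.** The two limbs meet where 0.8 × baseline = 100, at a baseline of 125. What a reading of 99 means depends on the starting value:

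| Baseline SBP | 20% line | Fall to reach 99 |
|---|---|---|
| 120 | 96 | 21 mm Hg (17.5%) |
| 110 | 88 | 11 mm Hg (10.0%) |
| 100 | 80 | 1 mm Hg (1.0%) |
| 99 | 79.2 | none |

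An event with no fall is therefore possible only when baseline is below 100. From 100 to 124 some fall is needed, though less than 20%.

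**Size for the maternal rule (illustration).**

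Inputs from the power analysis: 10-15% at 2.5 mg and 3-5% at the lower doses.

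Assumptions, not in the documents:
- 60 per group (180/3; the text also says 30 per group)
- both lower doses at the same rate
- a 2-df chi-square test at 0.05
- the stated rates taken as rates without automatic events
- a share b of women who start below 100 and have a later reading below 100

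Formulas:
- Rule as written: p′ = b + (1 − b)p.
- With a baseline condition, pessimistically allowing no 20% falls among low-baseline women: p″ = (1 − b)p.

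Example, b = 5%: p′ = 0.05 + 0.95 × 0.15 = 19.25%, against 0.05 + 0.95 × 0.03 = 7.85%. The ratio of rates drops from 15/3 = 5 to 19.25/7.85 = 2.45. Automatic events number 0.05 × 60 = 3 per group, against 0.03 × 60 = 1.8 expected events in a lower-dose group.

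Power from 400,000 simulated trials per setting, 60 per group:

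| b | 15% vs 3%, as written | 15% vs 3%, with condition | 10% vs 5%, as written | 10% vs 5%, with condition |
|---|---|---|---|---|
| 0 | 0.74 | 0.74 | 0.18 | 0.18 |
| 1% | 0.68 | 0.74 | 0.16 | 0.18 |
| 2.5% | 0.59 | 0.73 | 0.14 | 0.18 |
| 5% | 0.50 | 0.72 | 0.12 | 0.17 |

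With 30 per group, 15% versus 3% as written gives 0.40 at b = 0, then 0.35, 0.30 and 0.25. At 60 per group the conditioned rule does better than the written one in every setting with b above zero.

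**The case against.** The best defence is that both rules can be applied: every woman and every fetus can be classified. The protocol also speaks of incidence (Specific Aims) and of the development of these events (Experimental Design and Method), which suggests new events after the spinal. On that reading a woman at 98 before and after has developed nothing. This is probably what was meant, but the written definition does not require it, and whoever classifies events will work from the definition.

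The size rests on assumed inputs, and that stands. The documents give no baseline pressure distribution and name no chi-square test. If the stated rates already follow the written definition, nothing is lost relative to the plan, although the baseline condition would still help. A 5% share would then be impossible beside a 3% lower-dose rate.

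A reader might infer more than the documents support:

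- *That the rules are unworkable, or that a reading below 100 always counts without a fall.* Neither is so; the second holds only for baselines below 100.
- *That a dose effect on prolonged fetal falls is lost.* The continuous trace allows prolonged falls to be tabulated separately. What is missing is a statement of which limb is the endpoint.
- *That the fetal rule costs power.* Counting brief dips could dilute the contrast, but counting only sustained falls leaves fewer events. The direction is unknown, so no fetal figure is given.
- *That the fetal observation window is undefined.* The plan says "The data form is attached as Appendix B". That form is not in the text available for review and may settle the matter.

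**Conclusion.** The point holds as a minor one. The redundancy of the fetal duration limb and the missing baseline condition in the maternal limb both follow from the wording alone and need no assumption. The maternal flaw adds events that do not depend on dose; it weakens the comparison and favours no arm. Its size cannot be fixed from the documents. With an assumed 1% to 5% of women starting below 100, and the other assumptions listed above, power at 15% versus 3% falls from about 74% to between 68% and 50%. At 10% versus 5% power is only about 18% to begin with and falls to between 16% and 12%. For the fetal outcome the conclusion is only that the definition must say which event is primary.

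**What to change.** Make these changes for outcome classification only, before the pharmacy releases the syringe code. Treatment decisions are unaffected.

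1. **Fetal bradycardia.** Reconcile the two limbs by naming one as the primary event; the choice belongs to the investigators. Report by group, as separate categories, any fall below 110 bpm and falls below 110 bpm lasting more than 2 minutes.
2. **Maternal hypotension.** Count an SBP below 100 mm Hg as an event only when baseline SBP was 100 or above. Keep the 20% limb for all women. Report the definition as it now stands as a sensitivity analysis.

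The cost is rewording two definitions and adding some tabulation; the baseline pressure and the continuous trace are already collected. There are two downsides. The maternal rule gains a discontinuity at 100: a change from 100 to 99 counts, while 99 to 80 does not, because 0.8 × 99 = 79.2. And if the sustained fetal limb is chosen there will be fewer events, and their duration will partly reflect treatment, since "If hypotension and/or fetal bradycardia occur the patient will be treated with ephedrine, phenylephrine, nitroglycerin, or terbutaline as per our standard practice". Reporting both fetal categories avoids relying on either alone.

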## Significance:

Combined spinal epidural anesthesia (CSE) is a safe and simple procedure which provides adequate analgesia in laboring patients. Two possible complications of this technique are maternal hypotension and fetal bradycardia, which have been demonstrated to result from both rapid pain relief and sympathetic blockade. Untreated hypotension leads to diminished uteroplacental blood flow which could result in fetal hypoxia and acidosis.

Previous studies have determined the ED95 of bupivacaine to be 1.66 mg, less than the standard 2.5 mg being routinely given in CSE for laboring patients. It has also been demonstrated that half the typical dose of bupivacaine provides adequate pain relief in the majority of parturients. Whether the complication rate with a smaller dose of local anesthetic is diminished has yet to be determined.

We postulate that by reducing the amount of bupivacaine given in a CSE, maternal hypotension and fetal bradycardia will also be reduced, while still providing adequate analgesia. Prevention of these complications will lead to fewer rescues with sympathomimetic and uterine relaxation agents, fewer invasive treatments, and an increase in patient satisfaction.

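### Pain scores at 8 and 60 minutes cannot give the duration of spinal relief that outcome 4 claims, and the 60-minute score reflects the whole CSE package

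*Combined protocol and SAP*

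**What the plan says.** Specific Aims lists as outcome 4 "Adequacy and duration of pain relief following the spinal using a numeric pain rating scale from zero to ten". The objective it serves is narrower and does not mention duration: "The secondary objective is to evaluate the adequacy of pain relief with the reduced dose of spinal anesthetic". The hypothesis in Significance is that complications fall "while still providing adequate analgesia".

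Experimental Design and Method takes pain scores at baseline and at two times after the spinal: 8 minutes, described as "time to full effect of the spinal dose", and 60 minutes, described as "time when spinal dose could start wearing off". No later score is scheduled.

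Two epidural treatments run alongside. The first is universal: "All patients will be given our standard PCEA with a continuous infusion of 12ml/hr of 0.0625% bupivacaine with 2mcg/ml fentanyl". No start time is given. The second depends on pain: if relief is inadequate, "additional local anesthetic will be administered into the epidural catheter until the patient achieves comfort". The text gives no pain-score trigger and no time restriction for this.

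On recording, "The time of the spinal injection will be recorded". The printed data list asks for timing of the vasopressors and uterine relaxants but names no PCEA or top-up item. The data form itself (Appendix B) is not in the text supplied. Consent procedures also names the procedural anesthesia record as a data source. The Statistical Analysis section describes no analysis of pain and no rule for scores taken after a top-up.

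**The concern.** There are two separate difficulties.

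First, duration is a length of time, but the plan ties it to a pain scale read twice after the dose. That schedule gives pain status at two landmarks. It does not show when relief ended.

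Second, by the later landmark the score no longer belongs to the spinal alone. Top-ups are given in response to pain after randomization, so their frequency may differ by dose group. The protocol expects something of this kind: Potential health risks (under Consent procedures) and Risk to Benefit Ratio both name inadequate relief as the possible added risk of a lower dose. If more women in the low-dose groups are topped up to comfort before 60 minutes, the groups' scores are drawn together. A shorter block could then be reported as equal duration, an error that would favor the trial's own hypothesis.

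**Working it through.** The plan gives no figure for duration or for the pain analysis, and its power calculation does not address pain, so there is nothing to reproduce. The check sets the schedule against the outcome.

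**1. What two scores can resolve.** Inputs: post-dose scores at 8 and 60 minutes (Experimental Design and Method). Suppose a cut-off for adequate relief had been fixed. The number of classes for the end of relief is the number of post-dose scores plus one: 2 + 1 = 3.

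- At or before 8 minutes.
- Between 8 and 60 minutes, an interval 60 − 8 = 52 minutes wide.
- After 60 minutes, with no upper limit.

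Blocks ending at 10 and at 59 minutes fall in the same class, as do blocks ending at 61 and at 120 minutes. The plan chose 60 minutes as the point when wearing off could begin, so on its own premise many blocks may fall in the open-ended class.

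**2. What a top-up does to the class.** Take two hypothetical women. In one, the spinal fails at 40 minutes, she is topped up, and she is comfortable at 60. In the other, the spinal is still working at 60. Both give a low score at 60 minutes, and the pain scale puts both in the class after 60. For the first woman that is wrong. Without the time of the top-up the two cannot be told apart.

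**3. How much infusion could be present at each reading.** Inputs: 12 mL/h, 0.0625% bupivacaine = 0.625 mg/mL, fentanyl 2 mcg/mL (Experimental Design and Method). Start time *s*, in minutes after the spinal, is an assumption. Volume by time *t* = 12 × (t − s)/60 mL, or 0 if *t* ≤ *s*. Multiply by 0.625 for mg of bupivacaine and by 2 for mcg of fentanyl.

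| Assumed start (min) | By 8 min | By 60 min |
|---|---|---|
| 0 | 1.6 mL (1.0 mg, 3.2 mcg) | 12 mL (7.5 mg, 24 mcg) |
| 15 | 0 | 9 mL (5.6 mg, 18 mcg) |
| 30 | 0 | 6 mL (3.75 mg, 12 mcg) |
| 45 | 0 | 3 mL (1.9 mg, 6 mcg) |
| 60 | 0 | 0 |

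Patient demand doses and top-ups are extra. The table shows only that little or no infusion can have been given by 8 minutes, and that some will have been given by 60 unless the start is delayed to 60 minutes. It does not measure any effect on the score.

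**4. What is left intact.** The 8-minute score falls at the plan's stated full spinal effect and precedes nearly all epidural drug. It answers the secondary objective, which concerns adequacy. Hypotension and fetal bradycardia do not rest on the pain scores.

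**The case against.** The strongest reply is that little of the trial depends on this. Duration is one word in an outcome list, the secondary objective names adequacy only, and the study calls itself exploratory. Duration could be read as whether relief persists at a 60-minute landmark, and the hypothesis can be read as analgesia from the CSE as a whole. The infusion regimen is common to all groups and the study is double-blinded. This stands in part: it is why the 8-minute score and the primary objective are largely unaffected, and why the 60-minute comparison by randomized group remains valid for the CSE package. It does not rescue duration of relief from the spinal. The plan does not state the landmark reading, and under that reading comfort at 60 minutes may still come from a top-up. A common infusion does not make top-ups common.

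A second reply is that the two difficulties pull against each other: the more blocks outlast 60 minutes, the fewer wear-off top-ups occur before then. That is fair. Both can occur in the same trial, but the documents do not show how often either would.

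A reader might go further and infer that top-up and PCEA times are not collected. The documents do not support that. Appendix B is not available here and the anesthesia record may hold them, so this is a point to confirm. A reader might also take it as fact that every 60-minute score is taken under PCEA. That is a strong inference, since all women receive it and nothing in the text delays it, but no start time is stated.

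**Conclusion.** The point holds for the duration claim and for the interpretation of the 60-minute score, and should be corrected. As written, the measurement cannot deliver the stated outcome. At best it gives three classes, and only once a pain cut-off is supplied. The 60-minute score is a measure of combined spinal and epidural care.

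The direction of a possible bias is toward no difference between groups, on the assumption that women on lower doses are topped up more often before 60 minutes. Its size cannot be computed from the documents, and the infusion volumes above are not an estimate of it.

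It would be too strong to conclude that the pain assessment as a whole fails or that the secondary objective cannot be met: the 8-minute score serves adequacy with little or no epidural drug on board.

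**What to change.** 1. **Duration.** Either drop the word from outcome 4, or define it as time from spinal injection to first additional epidural dose. If it is kept, state the end of follow-up, censor at delivery, compare the randomized groups with a time-to-event method (for example Kaplan–Meier with a log-rank test), and describe the result as duration under the common background infusion.
2. **Adequacy.** Base it on the 8-minute score with a cut-off fixed in advance, counting any earlier epidural bolus as inadequate.
3. **60-minute score.** Report it as pain under combined spinal and epidural care, beside the proportion topped up by then in each group.
4. **Data.** Confirm that Appendix B or the anesthesia record holds PCEA start time, time of first additional epidural dose and delivery time; add whichever is missing.

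The cost is at most three time fields and a few sentences of definition. Injection time is already recorded, and no visit or procedure is added. Dropping the word costs less still, but leaves duration unstudied.

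Two limits remain. Demand-dose times may not be retrievable; in that case restrict the event to clinician boluses and say so, recognizing that demand doses could delay that event. And the new endpoint does not separate the spinal from the background infusion. No change to rescue treatment is proposed.

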## Significance:

Combined spinal epidural anesthesia (CSE) is a safe and simple procedure which provides adequate analgesia in laboring patients. Two possible complications of this technique are maternal hypotension and fetal bradycardia, which have been demonstrated to result from both rapid pain relief and sympathetic blockade. Untreated hypotension leads to diminished uteroplacental blood flow which could result in fetal hypoxia and acidosis.

Previous studies have determined the ED95 of bupivacaine to be 1.66 mg, less than the standard 2.5 mg being routinely given in CSE for laboring patients. It has also been demonstrated that half the typical dose of bupivacaine provides adequate pain relief in the majority of parturients. Whether the complication rate with a smaller dose of local anesthetic is diminished has yet to be determined.

We postulate that by reducing the amount of bupivacaine given in a CSE, maternal hypotension and fetal bradycardia will also be reduced, while still providing adequate analgesia. Prevention of these complications will lead to fewer rescues with sympathomimetic and uterine relaxation agents, fewer invasive treatments, and an increase in patient satisfaction.

## Experimental Design and Method:

The clinical trial will take place between January 1, 2014 to January 1, 2015 in the Labor and Delivery unit at the ***Roosevelt site of Mount-Sinai-Roosevelt Hospital Center.***

This randomized prospective double-blinded study is designed to investigate the development of maternal hypotension and fetal bradycardia in patients receiving CSE for labor analgesia. ***The target population are laboring patient admitted to the Labor and delivery unit. Any patient requesting an epidural for labor will be a potential candidate for this study.*** Discussion regarding the patient's participation in the trial will occur when she requests labor analgesia, as this is the customary first point of contact with the anesthesiology team. After informed consent and discussion of the technique for combined spinal-epidural, patients will be blindly randomized to one of three groups. ***The randomization will be done by blindly choosing one of these papers from the envelope, which will assign you to one of the three groups.***

These groups relate to the dose of bupivacaine that will be administered intrathecally during placement of the spinal anesthetic. Syringes will be prepared in advance by pharmacy containing one of the three doses of bupivacaine being identified only by a syringe number. Twenty micrograms of fentanyl is routinely administered in combination with bupivacaine in the spinal. ***The total amount in the syringe will be the same in the group, by adding saline when needed. Pharmacy will be providing us with prepared syringes containing either one of the 3 dosages of Bupivacaine for the spinal part of the combined spinal epidural (CSE). The syringes will be labeled with a number, and only pharmacy will know what concentration of bupivacaine is in the syringe. We will be given this information of what was in the syringe once final data are collected for the patients included in the study. The syringe will be prepared with a sterile technique, and the content will be ready to use as is by the anesthesia team providing the CSE.***

Group 1: 2.5 mg plain bupivacaine + 20 mcg fentanyl

Group 2: 1.66 mg plain bupivacaine + 20 mcg fentanyl

Group 3: 1.25 mg plain bupivacaine + 20mcg fentanyl

After randomization, a baseline pain score on a scale of 0-10 will be obtained. The fetal heart rate tracing will be recorded for 15 minutes with an external continuous heart rate monitor prior to placing the CSE in order to obtain an adequate baseline. Patients will be seated for the placement of the CSE. A blood pressure cuff and pulse oximeter will be in place and an initial blood pressure will be taken. The time of the spinal injection will be recorded. After placement of the CSE, the patient will be placed on her side, as is customarily done. Blood pressure will be taken every 2 minutes for 20 minutes and then every 15 minutes. A continuous fetal heart rate monitor will record the readings electronically. Blood pressure readings will be

recorded again at 60 minutes. All patients will be given our standard PCEA with a continuous infusion of 12ml/hr of 0.0625% bupivacaine with 2mcg/ml fentanyl.

If hypotension and/or fetal bradycardia occur the patient will be treated with ephedrine, phenylephrine, nitroglycerin, or terbutaline as per our standard practice. The dose and timing of this will be recorded.

Patients will also be asked to evaluate the effectiveness of their pain relief by asking them to rate their pain on a scale from 0-10 at 8 minutes (*time to full effect of the spinal dose*) and 60 minutes (*time when spinal dose could start wearing off*) following the spinal dose.

In the event that the patient does not receive adequate pain relief, additional local anesthetic will be administered into the epidural catheter until the patient achieves comfort.

The data form is attached as Appendix B.

Data collected will consist of:

- Demographics: Patient age, gestation, dilation in centimeters, gravity, parity
- Presence of labor induction/augmentation with Pitocin
- Maternal blood pressure- a baseline blood pressure and every 2 minutes for 20 minutes following the dose of spinal bupivacaine. A final blood pressure will also be recorded at 60 minutes.
- Fetal heart rate- a baseline fetal heart rate, and a continuous recording following the dose of spinal bupivacaine with an external monitor
- Cumulative ephedrine, phenylephrine, nitroglycerin, or terbutaline use and timing
- Pain scores at baseline, 8 minutes, and 60 minutes
- Delivery outcomes: normal spontaneous vaginal delivery, vacuum/forceps assisted vaginal, or caesarean section

Statistical Analysis:

Power analysis: As this is an exploratory but well controlled study, we will set the power at 0.9 and alpha at 0.05. 9 per group are required with an incidence fetal bradycardia/maternal hypotension of 7%; thus we will study 30 per group = 180 subjects. Accounting for dropouts and incomplete data, we seek to consent 200 patients. Published data estimates that the incidence of maternal hypotension after spinal bupivacaine is 10-15% at the higher 2.5 mg dose and likely reduced to 3-5% at the lower doses. The incidence of fetal bradycardia is less well studied but is estimated to occur in 3-7% of parturients after the higher 2.5mg bupivacaine dose. The occurrence of fetal bradycardia at lower doses of bupivacaine is not well studied but our prediction is that it will be reduced.

F tests- ANOVA: Repeated measures, between factors	Repetitions = 4
Analysis: A priori: Compute required sample size	Corr among rep measures = 0.5
Input: Effect size f = 1.2472191	Output: Noncentrality parameter λ =
a err prob = 0.05	Critical F = 5.143253
Power (1-err prob) = 0.90	22.399999
Number of groups = 3	

Numerator df = 2.000000  
Denominator df = 6.000000  
Sample size = 9  
Actual power = 0.903879  
Total sample size = 180

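### Assignment by a paper drawn from an envelope does not secure concealment and appears to precede the tracing that can exclude a woman; a pharmacy-held list of unique syringe numbers, used after eligibility is confirmed, would be better

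*Combined protocol and SAP*

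**What the plan says.** All the text on assignment is under Experimental Design and Method. The point of randomization is "After informed consent and discussion of the technique for combined spinal-epidural, patients will be blindly randomized to one of three groups", and the mechanism is "blindly choosing one of these papers from the envelope, which will assign you to one of the three groups". The three groups are then listed with their bupivacaine doses.

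The same section describes the masking of the syringes: "Syringes will be prepared in advance by pharmacy containing one of the three doses of bupivacaine being identified only by a syringe number"; "only pharmacy will know what concentration of bupivacaine is in the syringe"; "The total amount in the syringe will be the same in the group, by adding saline when needed"; and "We will be given this information of what was in the syringe once final data are collected for the patients included in the study".

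The procedure continues with "After randomization, a baseline pain score on a scale of 0-10 will be obtained", and the next sentence is "The fetal heart rate tracing will be recorded for 15 minutes with an external continuous heart rate monitor prior to placing the CSE". The stated purpose of that tracing is to give an adequate baseline. Under Human subjects, the exclusion criteria remove women whose tracing before the CSE is non-reassuring and women in whom a CSE cannot be performed. Under Consent procedures, the check made before a woman is approached is described for the inclusion criteria only.

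**The concern.** Masking a syringe and concealing an assignment are different safeguards. The first keeps the content of a chosen syringe hidden. The second keeps anyone from knowing or influencing which arm comes next. The protocol is specific about the first. On the second it offers a draw from an envelope and no sentence that connects the paper to a numbered syringe.

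Two separate risks would follow if the paper identifies the arm. Unblinding of the team would most expose the self-reported pain scores and the team's decisions to give vasopressors or uterine relaxants. Foreknowledge, or an unrecorded second draw, would threaten the comparability of the arms and so every outcome, including hypotension and fetal bradycardia.

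A different and smaller issue is timing. If the draw comes before the tracing, some women are randomized and then excluded for a reason that could have been known first. The plan has no stated rule for how those women are reported or analysed.

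**Working it through.** The plan gives no figure for allocation, and its only computed output, the ANOVA sample-size calculation, does not enter here. The check is therefore mainly a comparison of texts.

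**1. What the paper could carry.** Three readings are open.

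- *The group.* The group list gives the dose, so whoever sees the paper knows the arm while the woman can still be excluded. An unlogged redraw could be directed at an arm.
- *A code repeated for each dose.* The dose is not shown, but women sharing a code share a dose, so the code could be worked out from observed effects.
- *A code unique to the woman.* Neither unblinding nor directed redrawing follows. With masking intact, exclusions before injection cannot depend on arm.

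The text does not choose among these.

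**2. The order of steps.** Experimental Design and Method sets randomization after consent, then the pain score after randomization, then the tracing, then the CSE. Human subjects makes the tracing a ground for exclusion. Taken in sequence, the draw precedes the tracing. The link is inferred, because the words that place a step after randomization attach only to the pain score. The earlier check under Consent procedures does not settle it, since the tracing is an exclusion criterion.

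**3. Does the order change the numbers?** No. The power analysis counts 200 women consented. With exclusion rate e, the number dosed is 200 × (1 − e) whether exclusion falls before or after the draw. The documents give no value for e; at assumed rates of 2%, 5% and 10%, 4, 10 and 20 women are excluded. What changes is whether they are excluded before or after randomization.

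**4. How few events are at stake.** The power analysis puts hypotension at 10–15% with the highest dose and 3–5% with the lower doses. It gives both 30 per group and 180 in total (180/3 = 60 per arm), so both are shown.

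| Per arm | Highest dose | Lower dose | Difference (women) |
|---|---|---|---|
| 60 | 60 × 0.10 = 6 to 60 × 0.15 = 9 | 60 × 0.03 = 1.8 to 60 × 0.05 = 3 | 6 − 3 = 3 to 9 − 1.8 = 7.2 |
| 30 | 30 × 0.10 = 3 to 30 × 0.15 = 4.5 | 30 × 0.03 = 0.9 to 30 × 0.05 = 1.5 | 3 − 1.5 = 1.5 to 4.5 − 0.9 = 3.6 |

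These counts show why the integrity of assignment matters. They do not measure a bias.

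**The case against.** The strongest reply is that the text as a whole fits a code at least as well as a group name. The study is described as double-blind, syringes are known to the team only by number, and a team holding a paper with a group name could not pick a syringe without a further key or a call to pharmacy. The phrase about assigning a group may describe what the draw achieves rather than what is printed. The sentence also addresses the patient and refers to papers described nowhere else, so consent material outside the text reviewed may supply the link. This stands, and it is why no breach is alleged.

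It is also fair that the tracing's stated purpose is a baseline and that an earlier tracing could have served for screening. The order of draw and tracing remains an inference.

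A reader might go further and infer that the trial is unblinded, that allocation is being steered, or that a definite shift in the result can be calculated. Exchanging one woman who would become hypotensive on either dose for one who would not moves two events between two arms: 2/60 = 3.3 percentage points, or 2/30 = 6.7, against an expected difference of 10 − 5 = 5 to 15 − 3 = 12 points. The documents do not support using this as an estimate. It needs a paper that names the group, staff who redraw, and certainty about who will become hypotensive. It also assumes a contrast of two single arms, which the plan does not name; against the two lower doses pooled, the shift would be 1/60 + 1/120 = 2.5 points, or 1/30 + 1/60 = 5.0 points.

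The reply does not remove the gap. On the text available, nothing prevents the weaker readings, and the protocol does not say how an assignment reaches a syringe.

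**Conclusion.** The point holds as a cheap improvement to the method of assignment. Concealment is not secured by the written procedure. Whether that matters depends on what the paper carries: if it names the group, foreknowledge, redrawing and unblinding are all possible; if it is a unique code, what remains is avoidable exclusions after randomization, unrelated to arm, with no rule for handling them. That second cost also rests on the inferred order of draw and tracing. The size of any bias cannot be quantified from the documents. The change is worth making because it protects the trial whichever reading is right. Confidence is medium.

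**What to change.** Replace the envelope draw with a computer-generated randomization list held by pharmacy. The list links dose to syringe number and gives each woman a unique number; no number or code is repeated for a dose.

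Move the point of assignment. Complete the baseline pain score, blood pressure, 15-minute tracing and eligibility check first. Then take the next syringe in numerical order, immediately before CSE placement, and log it. A syringe taken but not injected is recorded and not reassigned.

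State the reporting rule: report every assigned woman by arm, including those in whom the CSE could not be performed, since reordering cannot prevent that exclusion. Analyse as randomized all who receive the spinal dose.

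The cost is protocol wording, a list and a log. Pharmacy already prepares and numbers the syringes, and the steps before the CSE are already in the protocol, so the added pharmacy and logging work should be small; the documents do not cost it. No additional consents are needed.
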